5.2 EXCLUSION CRITERIA

An individual who meets any of the following criteria will be excluded from randomization in this study. However, a Patient who fulfills the inclusion criteria but presents with any of the exclusion criteria would be enrolled in the registry (unfunded by PCORI).

1. Recent cardiovascular intervention within 30 days prior to randomization.
2. Presence of an existing TAVR or SAVR device
3. Pregnancy or lactation
4. Extreme or prohibitive TAVR or SAVR risk, adjudicated by the PSC review.
5. Active enrollment in another investigational study
6. Disproportionate TAVR vs SAVR risk, as adjudicated by the patient selection committee
7. Associated aortopathy ($AA \geq 45 \text{ mm}$ by maximal cross-sectional dimension, as confirmed by CT core laboratory analysis, or $AA < 45 \text{ mm}$ but site plan for surgery of the aorta in the event of randomization to surgery)
8. Site plan for treatment of concomitant non-coronary cardiovascular disease in the event of randomization to surgery (for instance, concomitant valve surgery, septal defect or coarctation repair, aorta or root replacement or repair)
9. In the presence of coronary artery disease deemed necessary for revascularization in the event of randomization to SAVR or TAVR, Syntax score ≥ 32 or deemed unsuitable for PCI, or deemed unsuitable for coronary artery bypass grafting (CABG).
10. Plan to use any device other than commercially approved Edwards balloon expandable or Medtronic self-expanding TAVR.
11. Leukopenia ($WBC < 3000 \text{ cells}/\mu\text{L}$), anemia ($Hgb < 8 \text{ g/dL}$), Thrombocytopenia ($Plt < 50,000 \text{ cells}/\mu\text{L}$) on latest available labs within 30 days prior to randomization.
12. Hemodynamic or respiratory instability requiring inotropic support, mechanical ventilation, or mechanical heart assistance within 30 days prior to randomization
13. $LVEF < 25\%$ within 90 days prior to randomization.
14. Stroke or transient ischemic attack (TIA) within 90 days prior to randomization
15. Renal insufficiency ($eGFR < 30 \text{ ml/min}$ per the Cockcroft-Gault formula)
16. Severe lung disease ($FEV1 < 50\%$ predicted), unresolved prior to randomization.
17. History of liver disease defined as MELD Score ≥ 10 or Child-Pugh Class B or C.
18. Unable to complete the KCCQ due cognitive impairment or other medical condition.

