6.2 MEASURES TO MINIMIZE BIAS: RANDOMIZATION

Patients will be randomized 1:1 to TAVR or SAVR using a centralized, secure web-based randomization system managed by the Data Coordinating Center, employing permuted blocks with varying block sizes and stratified by: (1) sex and (2) low or intermediate/high SAVR (clinical) risk and (3) planned TAVR type (in the event of randomization to TAVR). This is an open-label study; patients, treating clinicians, and site staff will not be blinded to treatment assignment. Randomization will be adaptive to maintain balance in study arm allocation within each site.

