8 STUDY ASSESSMENTS AND PROCEDURES

8.1 SCREENING/BASELINE

The following screening and baseline assessments should be conducted within 90 days of index procedure, unless otherwise noted. All assessments marked with an asterisk (*) are required prior to the patient selection committee.

- Signed Informed Consent*
- Demographics and Medical History*
- Physical Exam and vital signs*
- STS risk score and EuroSCORE II*
- SYNTAX score only in the presence of coronary artery disease requiring intervention*
- Concomitant Cardiovascular Medications*
- NIH Stroke Scale (NIHSS) and Modified Rankin Scale (mRS)
- Laboratory Test (Complete Blood Count, Comprehensive Metabolic Panel, and NT-proBNP). Sites who do not have the capability to collect an NT-proBNP lab, a BNP lab will be accepted instead *
- Pregnancy test (only for women of childbearing potential)
- Pulmonary Function Test (PFT) only for patients with a history of severe lung disease
- 12-lead ECG*
- Transthoracic Echocardiogram (TTE)*
- NYHA classification and CCS angina*
- 6 min walk test
- Frailty index (ADLs, 5 Meter Walk Test, and Grip Strength)*
- Kansas City Cardiomyopathy Questionnaire (KCCQ)
- SF-12 Questionnaire
- QOR-15 scale (Quality of recovery)
- PHQ-9 scale (Depression score)
- 3D Cardiac contrast CT within 1 year of case review committee date. If a TEE or a cardiac MRI are available per standard of care within 6 months of the patient selection committee date, the images will be collected for the study. *
- Iliofemoral CT Angiography within 1 year of case review committee date*
- Invasive or CT coronary Angiography within 1 year of case review committee date*
- Patient Selection Committee will be scheduled after completion of all of the above assessments marked with an asterisk (*)

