9.4.2 Analysis of The Primary Efficacy Endpoint(S)

The primary endpoint is a hierarchical composite of: (1) death within a shared follow-up period by a pair of patients, (2) disabling stroke within a shared follow-up period by a pair of patients, (3) non-disabling stroke within a shared follow-up period by a pair of patients, (4) valve reintervention within a shared follow-up period by a pair of patients, (5) rehospitalization (valve- or procedure-related, including heart failure, excluding valve reintervention within a shared follow-up period by a pair of patients; CEC adjudicated), and (6) unfavorable last available shared by a pair of patients KCCQ (VARC-3 definition: KCCQ <45 or decrease >10 points from baseline). This will be analyzed at latest available annual follow-up.

The primary analysis will use the unadjusted win ratio comparing all possible pairs of patients across treatment arms (one TAVR vs one SAVR), using the Finkelstein–Schoenfeld approach to prioritize more clinically important outcomes. For clinical event components, the pairwise comparison will consider both occurrence and timing of events, using all follow-up time within the PCORI-funded follow-up period that is common to both patients in the pair.

For the KCCQ component (lowest tier), the comparison will be based on whether the latest available KCCQ measurement for both patients (and occurring at least 1-year post-randomization) meets the unfavorable KCCQ definition. The win ratio will be reported with its 95% confidence interval, the p-value from the Finkelstein–Schoenfeld test, and a breakdown of wins/ties/losses at each hierarchical level.

As secondary analysis, the adjusted win ratio by stratification covariates will be performed. Adjustment method will be discussed in more details in the SAP.

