3. **Continuous endpoints** (e.g., KCCQ at each follow-up timepoint, SF-12 component scores, 6-minute walk distance, PHQ-9, time-averaged KCCQ): For longitudinal continuous outcomes, linear mixed models will be fitted with baseline outcome value, time as a categorical covariate, study arm and the interaction between treatment and time as fixed effects. Additionally, models will adjusted by the stratification factors. A subject-specific random effect will be included to describe the correlation between measures over time. Estimates will be presented as mean differences between study arms with 95% confidence intervals at prespecified timepoints. For change in ascending aorta dimension, time will be considered as a continuous covariate to estimate mean difference in annualized change

between study arms with 95% confidence interval. For time-averaged KCCQ, linear regression will be fitted with treatment as main covariate adjusted by the stratification factors. Mean difference between study arms will be presented with 95% confidence interval.

4. **Rate/count endpoints** (e.g., cardiovascular rehospitalization days): Negative Binomial model will be fitted with study arm as main covariate adjusted by the stratification factors and offset by days alive and out of hospital. Incidence rate ratio between study arms will be estimated with 95% confidence interval.

9.4.4 **Multiplicity and Control of Type I Error**

Multiplicity and Control of Type I Error. To control the overall family-wise type I error rate at two-sided $\alpha = 0.05$, hypothesis testing will follow a prespecified gatekeeping (hierarchical) procedure. First, the primary endpoint will be tested at two-sided $\alpha = 0.05$. Only if the primary endpoint is statistically significant will the key secondary endpoint be tested at two-sided $\alpha = 0.05$. Only if both the primary and key secondary endpoints are statistically significant will confirmatory testing proceed to a prespecified family of additional secondary endpoints.

For this family of additional secondary endpoints, multiplicity will be controlled using the Holm step-down procedure at two-sided $\alpha = 0.05$. The set of endpoints included in the Holm family (and any prespecified rules for missing data and estimands) will be fully specified in the Statistical Analysis Plan.

9.4.5 **Safety Analyses**

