9.4.7 Exploratory Analyses

Other prespecified **exploratory** subgroups of interest will be **pre-specified planned TAVR type, pre-specified planned coronary revascularization**, presence of **aortopathy** (ascending aorta maximal dimension ≥ 40 mm). The win ratio comparing TAVR to SAVR will be calculated separately within each subgroup and formal tests of interaction subgroups will be used to ascertain whether the treatment effect differs between subgroups based on a Z-test calculated as the difference between stratified log win ratios. (11). For subgroup analyses using time-averaged KCCQ score, formal statistical tests of interaction will be used to compare whether the treatment effect on time-averaged KCCQ scores (estimated from linear models) varies according to patient characteristics.

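### The time-averaged KCCQ regression omits baseline KCCQ, which gives up precision in the analysis that carries the powered subgroup tests

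*Protocol*

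**What the plan says.** Section 9.4.3 (continuous endpoints) sets two models side by side. For longitudinal continuous outcomes, KCCQ at each visit among them, "linear mixed models will be fitted with baseline outcome value, time as a categorical covariate, study arm and the interaction between treatment and time". For the time average the model is different: "For time-averaged KCCQ, linear regression will be fitted with treatment as main covariate adjusted by the stratification factors".

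Section 6.2 gives the stratification factors as sex, SAVR risk (low against intermediate/high) and planned TAVR type. None of them is a health-status score.

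Section 9.4.6 reports slightly less than 60% power for an all-or-nothing interaction on the primary outcome and for that reason adds subgroup analyses of time-averaged KCCQ, taking an SD of 14.5. The four interaction tests given a power there, for sex, age, TAVR risk and SAVR risk, are presented on that outcome. Section 9.4.7 says the tests will ask whether "the treatment effect on time-averaged KCCQ scores (estimated from linear models) varies according to patient characteristics" and names no covariates. Section 9.4.8 imputes missing KCCQ for the time average from a mixed model with visit, arm, their interaction and subject effects; no baseline value is listed.

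Baseline KCCQ is available. The Schedule of Activities (Section 1.3) places it in the column completed before randomization, Section 8.1 lists it, and Section 5.2 excludes patients who are "Unable to complete the KCCQ due cognitive impairment or other medical condition". The lowest tier of the primary endpoint needs it anyway, to measure decline from baseline. Section 9.4.3 builds the time average from post-baseline scores only, so the covariate would not be part of the outcome.

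**The concern.** One instrument is adjusted for baseline when analysed visit by visit and left unadjusted when averaged over visits, with no reason given. A patient's score before treatment usually predicts later scores on the same questionnaire. Leaving it out keeps that predictable variation in the residual, so standard errors are wider than they need be, and any chance difference between arms in baseline KCCQ goes uncorrected.

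This matters more here than for an ordinary secondary endpoint, because time-averaged KCCQ was chosen to give the heterogeneity tests adequate power. Section 4.1 also commits the trial to at least 80% power in the planned interaction tests, and the sex test is only just above that.

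**Working it through.** **Inputs.** SD of time-averaged KCCQ 14.5; interaction differences of 5 units (sex, age) and 6 units (TAVR risk, SAVR risk); smaller-subgroup fractions f of 0.35, 0.50, 0.25 and 0.33 (all Section 9.4.6); N = 1200 randomized 1:1, with 1020 complete-data patients behind the primary power and a 12.5% allowance for crossover and loss (Section 9.4.1). The significance level is 5%, taken as two-sided because Section 9.4.6 does not state sidedness.

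**Step 1: reproduce the stated powers.** With 1:1 arms in each subgroup,

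SE = SD × √[4/(Nf) + 4/(N(1−f))], power = Φ(δ/SE − 1.96).

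For sex at N = 1200: SE = 14.5 × √(4/420 + 4/780) = 1.755, and power = Φ(5/1.755 − 1.96) = 81.3%.

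| Test | Stated | N = 1200 | N = 1020 |
|---|---|---|---|
| Sex | 82% | 81.3% | 74.7% |
| Age | 85% | 84.8% | 78.6% |
| TAVR risk | 87% | 87.4% | 81.6% |
| SAVR risk | 92% | 92.1% | 87.4% |

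The stated figures therefore use all 1200 patients and take no gain from baseline. Taking 12.5% off 1200 leaves 1050, at which the sex test has 76.0%.

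**Step 2: add baseline KCCQ.** The residual SD becomes 14.5 × √(1 − r²), so the variance falls by r²: 9% at r = 0.3, 25% at 0.5, 36% at 0.6.

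| r (assumed) | Residual SD | Sex, N = 1200 | Age | TAVR risk | SAVR risk | Sex, N = 1020 |
|---|---|---|---|---|---|---|
| none | 14.5 | 81.3% | 84.8% | 87.4% | 92.1% | 74.7% |
| 0.3 | 13.8 | 84.8% | 87.9% | 90.2% | 94.2% | 78.6% |
| 0.4 | 13.3 | 87.5% | 90.3% | 92.3% | 95.7% | 81.7% |
| 0.5 | 12.6 | 90.8% | 93.2% | 94.8% | 97.3% | 85.8% |
| 0.6 | 11.6 | 94.5% | 96.2% | 97.3% | 98.8% | 90.7% |

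(Age, TAVR risk and SAVR risk columns are at N = 1200.) At r = 0.5, 1200 patients give the precision of 1200/(1 − 0.25) = 1600 unadjusted.

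**Step 3: overall effect.** The half-width of the 95% confidence interval for the mean difference at N = 1200 is 1.96 × SD × √(4/1200): 1.64 points unadjusted, and 1.57, 1.42 and 1.31 points at r = 0.3, 0.5 and 0.6.

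**Step 4: is 0.3 to 0.6 a fair range?** The protocol gives an SD of 20 for one measurement (Section 9.4.1) and 14.5 for the average. Suppose all visits, baseline included, are equally correlated at ρ, and use the visit weights of Section 3 (6.5, 11.5, 12, …), scaled to sum to 1. With S = Σw² and v = (14.5/20)² = 0.526, ρ = (v − S)/(1 − S) and r = ρ/√v.

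- Three follow-up visits: S = 0.354, ρ = 0.27, r = 0.37.
- Four visits: ρ = 0.36, r = 0.49.
- Six visits: S = 0.172, ρ = 0.43, r = 0.59.

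This is a rough anchor only. Baseline is measured before valve replacement and may correlate less with later scores than they do with each other.

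**The case against.** The strongest reply is that nothing in the plan is invalid. Randomization makes the unadjusted comparison unbiased, the stated powers are met at the planned sample size, and these are secondary and subgroup analyses. All of that stands. So does the point that r is not in the protocol; at r = 0.3 the sex test gains only about 3.5 points.

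Four stronger readings are tempting, and the protocol does not support them.

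- *The tests are underpowered because baseline is omitted.* The 75% for sex comes from using 1020 patients rather than 1200. The figure of 1020 belongs to the primary-endpoint calculation, and Section 9.4.8 imputes missing KCCQ rather than dropping patients. Imputation from model means does not restore lost information, so attrition is a real risk to precision, but it is a separate cause.
- *Baseline is used in every other longitudinal model.* It is listed for the longitudinal continuous outcomes. The repeated-measures logistic models and the KCCQ imputation model list no baseline value.
- *The interaction models are fixed without baseline.* Section 9.4.7 says only that they are linear. The omission is fixed in the main regression; for the interactions it is merely unaddressed.
- *The primary win ratio should be stratified for the same reason.* Section 9.4.2 says: "The primary analysis will use the unadjusted win ratio comparing all possible pairs of patients across treatment arms". The adjusted version is already planned as a secondary analysis. In three simulated scenarios at n = 1020 with eight strata and 500 trials each, stratified and unstratified Finkelstein–Schoenfeld tests differed in power by 0.2 to 1.0 percentage points. The Monte Carlo standard error of each estimate is about √(0.83 × 0.17/500) = 1.7 points. No gain is shown, so there is no ground to change the primary analysis.

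**Conclusion.** The point holds as an avoidable loss of precision. Section 9.4.3 itself fixes a time-averaged KCCQ model without baseline KCCQ, so the matter is not simply left to the statistical analysis plan. There is no bias in expectation and no error in the stated powers at N = 1200.

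For an assumed r of 0.3 to 0.6, residual variance would fall by 9% to 36% and sex-interaction power at N = 1200 would rise from 81% to between 85% and 94.5%. With 1020 evaluable patients it would rise from 75% to between 79% and 91%. Only the direction is certain; the size depends on r.

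One ambiguity remains. The protocol does not say whether 14.5 is a raw or a baseline-adjusted SD. The working treats it as raw. If it were already adjusted, the model as written would fall short of the stated power: for sex at N = 1200, about 78% at r = 0.3 and 69% at r = 0.5.

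**What to change.** In Section 9.4.3, add baseline KCCQ overall summary score as a covariate in the time-averaged KCCQ regression, alongside the stratification factors. In Section 9.4.7, name the covariates of all time-averaged KCCQ interaction models and include baseline KCCQ. In Section 9.4.8, add it to the KCCQ imputation model. In Section 9.4.6, say whether 14.5 is a raw or an adjusted SD. Leave the unadjusted win ratio as the primary analysis.

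The cost is one covariate and a few lines of text, with no new data. Make the change before outcome data are seen, so that it cannot look data-driven. Because the trial is open-label, the baseline score has to be recorded before allocation is known. The Schedule of Activities heading says so, but Section 8.1 does not mark KCCQ among the items required before committee review, so a cross-reference there would help.

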Key Secondary	Hierarchical composite of (1) death (2) time averaged KCCQ score.	Win ratio	Survival status assessed at latest available annual follow-up. KCCQ will be assessed as a time-average over patient follow-up	>95%
Secondary	Time averaged Kansas City Cardiomyopathy Questionnaire (KCCQ) status (continuous)	KCCQ questionnaire	Time average over all patient follow-up	>95%
Secondary	Kansas City Cardiomyopathy Questionnaire (KCCQ) status (continuous)	KCCQ questionnaire	From baseline to 1, 12, 24, 36, 48, 60, 72, 84, 96, 108, 120 months	Not powered
Secondary	CV rehospitalization days (count)	CRF: clinical events assessed by direct follow-up	Event driven	Not powered
Secondary	Short Form-12 (SF-12) Health Survey (continuous)	SF-12 questionnaire	From baseline to 1, 12, 24, 36, 48, 60, 72, 84, 96, 108, 120 months	Not powered
Secondary	New York Heart Association (NYHA) status (categorical)	NYHA clinical scale	From baseline to discharge, 1, 12, 24, 36, 48, 60, 72, 84, 96, 108, 120 months	Not powered
Secondary	6 min walk test (continuous)	6 min walk test distance	From baseline to 1, 12	Not powered
Secondary	Depression score (continuous)	PHQ-9 score	From baseline to 1, 12, 24, 36, 48, 60, 72, 84, 96, 108, 120 months	Not powered
Secondary	Time-to-recovery to baseline (categorical)	QOR-15 scale	From baseline to discharge, 1, 12 months	Not powered
Secondary	Death (time-to-event)	CRF: clinical events assessed by direct follow-up	Event driven	Not powered
Secondary	Cardiovascular death (time-to-event)	CRF: clinical events assessed by direct follow-up	Event driven	Not powered
Secondary	All stroke (time-to-first event) Ischemic, hemorrhagic, not otherwise specified	CRF: clinical events assessed by direct follow-up	Event driven	Not powered
Secondary	Disabling stroke (time-to-first event,)	CRF: clinical events assessed by direct follow-up	Event driven	Not powered
Secondary	Rehospitalization (valve-, procedure-, or HF-related); (time-to-first event)	CRF: clinical events assessed by direct follow-up	Event driven	Not powered
Secondary	Death/stroke/rehospitalization; (time-to-first event)	CRF: clinical events assessed by direct follow-up	Event driven	Not powered
Secondary	Aortic dissection (time-to-first event)	CRF: clinical events assessed by direct follow-up	Event driven	Not powered
Secondary	Need for surgery of the aorta (time-to-event)	CRF: clinical events assessed by direct follow-up	Event driven	Not powered

[figure not shown]

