 48-month assessment = weight of 12 (representing KCCQ between 42 months and 54 months),
 60-month assessment = weight of 12 (representing KCCQ between 54 months and 66 months),
 72-month assessment = weight of 12 (representing KCCQ between 66 months and 78 months),
 84-month assessment = weight of 12 (representing KCCQ between 78 months and 90 months),
 96-month assessment = weight of 12 (representing KCCQ between 90 months and 102 months),
 108-month assessment = weight of 12 (representing KCCQ between 102 months and 114 months),
 120-month assessment = weight of 12 (representing KCCQ between 114 months and 126 months)

Secondary Endpoints (Patient-centered and Clinical)

Patient-reported outcomes / functional outcomes

These are assessed as shown in Table 1 :

- **Time-averaged KCCQ:** time-weighted mean of KCCQ overall summary score across available follow-up timepoints.
- **KCCQ status (serial):** KCCQ overall summary score at discharge and prespecified follow-up visits.
- **SF-12:** Physical and Mental Component Summary scores at prespecified visits.
- **NYHA class:** NYHA I–IV at prespecified visits.
- **6-minute walk test:** distance (meters) at prespecified visits.
- **PHQ-9:** depression score (0–27) at prespecified visits.

- **Time-to-return to baseline (QOR-15):** time from index procedure to first follow-up at which QOR-15 returns to (or exceeds) the patient's pre-procedure baseline (operational rules and handling of missingness specified in SAP).

Additional clinical endpoints

- **Death (time-to-event)**, cardiovascular death (time-to-event)
- **All stroke, disabling stroke** (time-to-first event).
- **Rehospitalization** (time-to-first event), as defined above.
- **Composite of death/stroke/rehospitalization:** time to first occurrence of any of death, any stroke, or rehospitalization (time-to-first event), as defined above.
- **Aortic dissection (time-to-first-event):** imaging-, operative-, or autopsy-confirmed aortic dissection after randomization.
- **Need for surgery of the aorta (time-to-first-event):** any open or endovascular surgical procedure to repair/replace the ascending aorta/aortic root after randomization (including concomitant or follow-up procedures).
- **CV rehospitalization days:** cumulative number of inpatient hospital days for cardiovascular causes over follow-up (CEC adjudication rules and counting conventions will be specified in the SAP and CEC charter).

Secondary Imaging Endpoints

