6.0 STUDY INTERVENTION

6.1 STUDY INTERVENTION(S) ADMINISTRATION

6.1.1 Study Intervention Description

The study intervention(s) (TAVR vs SAVR) are standard of care procedures performed with FDA-approved commercially available devices. Time between randomization and planned date of intervention should be 2 weeks or less.

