9.3 POPULATIONS FOR ANALYSES

Intention-to-Treat (ITT) Analysis Dataset: All randomized patients analyzed according to their originally assigned treatment group, regardless of whether they actually received the assigned treatment, had treatment cross-over or protocol deviation, were lost to follow-up or partially withdrawn from the study.

As treated (AT) Analysis Dataset: All randomized patients analyzed according to the initial treatment actually received (TAVR or SAVR), irrespective of randomization assignment.

Safety Analysis Dataset: All randomized patients in whom the assigned valve-replacement procedure is initiated. Patients will be analyzed according to the procedure actually received.

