Disabling stroke (stroke with disability)	mRS ≥2 at 90 days and increase ≥1 category from pre-stroke baseline. (mRS ideally at 90 days; 30–90 days acceptable.)	VARC-3 Table 3
Non-disabling stroke	mRS 0–1 at 90 days or no increase in mRS category from pre-stroke	VARC-3 Table 3

Term	Definition	Reference / Justification
(stroke without disability)	baseline.	
Hospitalization / rehospitalization (overall)	Any admission after index hospitalization/study enrolment to an inpatient unit/ward for ≥ 24 h, including an ED stay. Planned admissions for pre-existing conditions excluded unless worsening. ED/urgent care < 24 h may count only if substantive intensification of therapy occurs (e.g., IV diuretics, major med escalation, addition of new agents).	VARC-3 Table 4
Procedure-related or valve-related hospitalization	Includes hospitalization for new complications (e.g., stroke, bleeding, pericardial effusion, vascular/access complication, conduction disturbance/arrhythmia, AKI), deterioration of prior periprocedural complications, BVD (PVR, thrombosis, endocarditis, SVD/NSVD), or valve/procedure-related HF.	VARC-3 Table 4
Bleeding (VARC-3 “overt bleeding” framework)	“Overt bleeding” = clinically obvious source or source identified after appropriate evaluation; procedural blood loss counts as overt bleeding. Bleeding is graded as VARC Types 1–4.	VARC-3 Table 5
Bleeding Type 1	Overt bleeding requiring medical evaluation and leading to hospitalization/increased level of care OR transfusion of 1 unit RBC/whole blood.	VARC-3 Table 5
Bleeding Type 2	Overt bleeding requiring 2–4 units transfusion OR hemoglobin drop > 3 g/dL but < 5 g/dL.	VARC-3 Table 5
Bleeding Type 3	Overt bleeding in critical organ; or causing hypovolemic shock/severe hypotension requiring vasopressors/surgery; or requiring reoperation/re-intervention; or chest tube output ≥ 2 L/24h; or transfusion ≥ 5 units; or hemoglobin drop ≥ 5 g/dL.	VARC-3 Table 5
Bleeding Type 4	Overt bleeding leading to death.	VARC-3 Table 5
Vascular complications (major)	Includes aortic dissection/rupture; vascular injury (arterial/venous) or compartment syndrome resulting in death, VARC bleeding \geq Type 2, limb/visceral ischemia, or irreversible neurologic impairment; distal embolization causing death/amputation/ischemia/irreversible damage; unplanned endovascular/surgical intervention with those consequences; or closure device failure with those consequences.	VARC-3 Table 6

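### The offset for CV rehospitalization days subtracts the counted days from their own exposure, so the reported ratio is not a rate ratio per day of follow-up (minor)

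*Protocol*

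**What the plan says.** Section 3 (Additional clinical endpoints) defines the outcome as the "cumulative number of inpatient hospital days for cardiovascular causes over follow-up". It is a duration, not a number of admissions. Table 1 in section 1.1 lists it as a secondary count endpoint that is not powered.

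Section 9.4.3, item 4, fixes the model: a "Negative Binomial model will be fitted with study arm as main covariate adjusted by the stratification factors", "offset by days alive and out of hospital". It also fixes the effect measure: "Incidence rate ratio between study arms will be estimated with 95% confidence interval".

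Section 3 leaves the adjudication rules and counting conventions for the outcome to the SAP and the CEC charter. It does not defer the offset. The protocol gives neither the date from which days alive and out of hospital are counted nor a rule for a patient who has none.

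**The concern.** In a log-link count model the offset should be the log of the time during which the counted thing could occur. A hospital day can occur on any day that the patient is alive and followed. Time out of hospital is a sensible exposure for a count of admissions, because a patient already in hospital cannot be admitted again. It does not suit a count of days in hospital, because every counted day falls on a day that the offset leaves out.

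Two things follow. The coefficient for study arm compares hospital days per day out of hospital, which is not what the label incidence rate ratio conveys. The exposure also becomes an outcome of treatment: as worded, it removes CV days, non-CV days and possibly the index stay. Section 2.3.1 itself says that procedural recovery is shorter after TAVR than after SAVR, so the denominator may differ by arm for reasons unrelated to rehospitalization.

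At stake is the meaning of one secondary result. Under section 9.4.4 it could enter the Holm family if the SAP places it there and both the primary and key secondary tests succeed.

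**Working it through.** The protocol gives no rate, power or expected mean for this endpoint, so there is no planned figure to reproduce. Mean days and lengths of stay below are assumptions.

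**Notation.** T is days alive in follow-up and H is hospital days. To isolate the effect, all hospital days are taken as CV days and the index stay is ignored. The protocol's offset is read as log(T − H), as a log link requires.

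**Single patient.** The model scales H by T − H instead of by T, so the patient's rate is inflated by T/(T − H).
- 30 of 365 days: 30/365 = 0.082 against 30/335 = 0.090, a factor of 1.09.
- 200 of 365 days: 200/365 = 0.548 against 200/165 = 1.212, a factor of 2.21.
- 60 of 90 days (extreme, early death): 60/90 = 0.67 against 60/30 = 2.0, a factor of 3.

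**Between arms.** With mean days H0 and H1 and common T, the true ratio H1/H0 is multiplied by (T − H0)/(T − H1). All rows have a true ratio of 1.333.

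| Mean days H0 vs H1 | T = 365 | T = 1095 | T = 2190 |
|---|---|---|---|
| 3 vs 4 | 1.337 | 1.335 | 1.334 |
| 30 vs 40 | 1.374 | 1.346 | 1.340 |
| 120 vs 160 | 1.593 | 1.390 | 1.360 |

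For example, 30 vs 40 days at T = 1095 gives 1.333 × 1065/1055 = 1.346, and 120 vs 160 days at T = 365 gives 1.333 × 245/205 = 1.593.

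**Simulation.** The algebra uses arm means, whereas the model uses each patient's own offset. Sixty trials were therefore simulated for each of two assumed mean stays. Each had 600 patients per arm over 3 years, with death at 5.3% and 7.1% and rehospitalization at 9.3% and 12.5% (SAVR and TAVR, section 9.2, Table 2). A negative binomial model was fitted with each offset.
- 8-day stays: geometric mean ratio 1.388 with T, 1.381 with T − H.
- 30-day stays: 1.334 with T, 1.342 with T − H.
- Largest shift in a single trial: 0.14 and 0.22 on the log scale, factors of about 1.15 and 1.24.

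There was almost no systematic bias, but a single trial's estimate could move noticeably.

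**When the offset fails.** log(T − H) is undefined only when days alive and out of hospital equal exactly zero.
- A patient who dies during a later readmission has been home in between, so the offset is finite.
- A patient who dies before first discharge has zero such days if time starts at the procedure or index admission.
- If time starts at randomization, section 6.1.1 matters: "Time between randomization and planned date of intervention should be 2 weeks or less". Days at home before the procedure then make the offset finite for that patient too. Zero would need an unbroken hospital stay from randomization to death.

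**The case against.** The strongest reply is that this hardly matters. CV hospital days per day at home is a definable quantity. If hospital use and survival are the same in both arms, the ratio is still 1, so the offset does not by itself create a difference. With short stays the ratio moves only in the third decimal place or by about 1%. The 1.593 in the table needs mean hospital days of 120 and 160 within one year, which is implausible beside assumed rehospitalization rates of 9.3% and 12.5%. All of this stands, and it sets the severity. It does not make the label correct, and it does not remove the dependence of the denominator on treatment.

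A reader might infer more: that the offset is undefined for anyone who dies in hospital, so the model discards peri-procedural deaths. By assuming that 1% to 2% die in the index stay, one could count 6 to 12 of 600 patients lost per arm. The documents do not support this. They give no index-stay mortality, and the count needs time to start at the procedure or index admission, which the protocol does not say. Appendix B counts as rehospitalization "Any admission after index hospitalization/study enrolment to an inpatient unit/ward", so a patient who dies in the index stay would normally contribute no outcome days anyway. What remains is narrower: the intention-to-treat set is "All randomized patients analyzed according to their originally assigned treatment group", and a patient with zero exposure could not enter the model.

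A convention for zero exposure could be left to the SAP. The choice of offset was not left to it.

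**Conclusion.** The offset in section 9.4.3 is wrong for this outcome as written. It removes the counted days from the exposure, so the estimate is hospital days per day out of hospital, while the plan reports an incidence rate ratio. It also conditions on a quantity that treatment can affect.

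The expected size is small: 1.333 becomes about 1.335 to 1.346 at 3 years for mean days from 3 vs 4 up to 30 vs 40. It is larger with heavy hospital use or short follow-up, and a few patients with long stays and early death can shift a single trial's estimate. These figures rest on assumed mean days and stays. The algebra also leaves out non-CV days and the index stay.

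The problem of an undefined offset is confined to patients with exactly zero days alive and out of hospital, and whether there are any depends on the unstated time origin.

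Severity is minor: the endpoint is secondary and not powered, and neither the primary nor the key secondary conclusion depends on it.

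**What to change.** In section 9.4.3, item 4, replace the offset with the log of days alive under follow-up, counted from randomization to death or censoring. The reported ratio then is CV hospital days per day of follow-up, and the time origin is stated. Counting the day of randomization as day 1 gives every randomized patient a positive exposure. This also agrees with section 9.4.5, which already expresses adverse event rates per patient-year. If days alive and out of hospital are of interest, keep them as a separate outcome and not as the denominator.

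The cost is a few words in the protocol and the matching line in the SAP. The model, the covariates, the sample size and the data to be collected stay the same.
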